NON-INTERVENTIONAL STUDY PROTOCOL

PRODUCT: OBIZUR® [ANTIHEMOPHILIC FACTOR (RECOMBINANT), PORCINE SEQUENCE]

STUDY TITLE: POST-MARKETING non-interventional safety evaluation of obizur in the treatment of bleeding episodes for patients with acquired hemophilia A

PROTOCOL IDENTIFIER: 241302

VERSION: 11 MAR 2015

Study Sponsor: Baxalta U.S. Inc. Baxalta Innovations GmbH

[name] [name]
[name]

TITLE PAGE: POST MARKETING SAFETY STUDY

PROTOCOL TITLE	Post Marketing Non-Interventional Safety Evaluation of Obizur in the Treatment of Bleeding Episodes for Patients with Acquired Hemophilia A						
PROTOCOL ID #	241302						
ORIGINAL	2015 MAR 11						
OTHER REGISTER	Study not registered						
MEDICINAL PRODUCT	,						
Active Ingredient(s)	Antihemophilic Factor (Recombinant), Porcine Sequence						
Medicinal Product	Antihemophilic Factor (Recombinant), Porcine Sequence						
PRODUCT REF. #	NA						
PROCEDURE #	NA						
MARKETING AUTHORISATION HOLDER (MAH)	Baxalta U.S. Inc. [name] Baxalta Innovations GmbH [name]						

RESEARCH QUESTION & OBJECTIVES

The overall objective is to assess data on aspects of safety, treatment, and treatment outcomes among patients with acquired hemophilia A (AHA) who are prescribed and treated with Obizur in a real-world setting.

Research Question

The study is designed to assess safety and to describe factors related to the safety, utilization and effectiveness of Obizur in real-world clinical practice.

Primary Objective

The primary objective is to determine the incidence of therapy-related SAEs in patients with AHA who are prescribed and treated with Obizur in routine clinical practice.

Secondary Objective(s)

- 1. To describe hemostatic effectiveness of Obizur in the treatment of bleeding episodes.
- 2. To describe the frequency, total dose, and total number of infusions of Obizur required to control bleeding episodes.
- 3. To describe concomitant medication use.
- 4. To describe the clinical setting in which patients first present with symptoms of AHA, patient comorbidities, time from presentation of symptoms to a positive diagnosis, and time from a positive diagnosis to first treatment with Obizur.
- 5. To describe the immunogenicity of Obizur during the course of treatment.

COUNTRY OF STUDY	United States
AUTHOR	, MD [name]

2. LIST OF ABBREVIATIONS

Abbreviation	Definition
AE	adverse event
AHA	acquired hemophilia A
aPPCs	activated prothrombin complex concentrates
B19V	parvovirus B19
ВНК	baby hamster kidney
CRF	case report form
CSR	case study report
DDVAP	Demopressin
EC	ethics committee
EDC	electronic data capture
ELISA	enzyme-linked immunosorbent assay
F	Factor
FDA	Food and Drug Administration
HAV	hepatitis A virus
HBV	hepatitis B virus
HCV	hepatitis C virus
HEV	hepatitis E virus
HIV	human immunodeficiency virus
ICF	informed consent form
IRB	institutional review board
МАН	marketing authorization holder
MedDRA	medical dictionary for regulatory activities
NMC	non-medical complaint
pFVIII	porcine FVIII
rFVIIa	recombinant activated FVII
rpFVIII	Recombinant pFVIII
SAE	serious adverse event
SAER	serious adverse event report
SIC	subject identification code
U	Units
WHO	World Health Organization
· · · · · · · · · · · · · · · · · · ·	

3.2 Investigator(s)

The name and contact information of all investigators will be maintained by the MAH in a separate file and provided to the individual investigators (see Annex 14.1).

3.3 Other Individuals Involved in the Study

The name and contact information of other individuals involved with the study (e.g., MAH's medical expert and study monitor, MAH's representative(s), laboratories, steering committees, and oversight committees (including ethics committees [ECs]), as applicable) will be maintained by the MAH and provided to the investigator (see Annex 14.1).

4. ABSTRACT

Title:

Post Marketing Non-Interventional Safety Evaluation of Obizur in the Treatment of Bleeding Episodes for Patients with Acquired Hemophilia A

Rationale and background:

Acquired hemophilia A (AHA) is a rare autoimmune disorder in which non hemophilic persons develop auto-antibodies directed against circulating blood coagulation factor (F) VIII. These auto-antibodies are distinct from the alloantibodies that form in patients with congenital hemophilia A in response to factor replacement therapy. In approximately 50% of cases FVIII autoantibodies occur in patients with no concomitant disease, while the remaining cases may be associated with an underlying medical condition such as pregnancy, hematological or solid tumors, infections, use of medications, or autoimmune diseases such as systemic lupus erythematosus, rheumatoid arthritis, and thyroid disorders. The estimated incidence rate of AHA is approximately one case per million persons annually, though it is likely that this figure is underestimated in the elderly population. This presumption is underscored by evidence indicating that the incidence of AHA increases with age. The incidence rate in children under 16 years is estimated to be 0.045 per million persons annually, compared to an estimated rate of 14.7 per million persons annually in individuals over the age of 85 years.

A recently developed highly purified antihemophilic recombinant porcine sequence FVIII therapy (Obizur®) was approved for marketing for the treatment of AHA. While data from the clinical trial on Obizur demonstrated a positive safety and efficacy profile of porcine FVIII (pFVIII) in patients with AHA after 90 days, additional data are needed regarding longer-term safety (up to 180 days post-treatment), utilization, and the effectiveness of pFVIII in the real-world setting. Therefore, Baxalta plans to conduct the present study to assess safety of Obizur based on incidence of serious adverse events (SAEs), and to describe the hemostatic effectiveness of Obizur in the treatment of bleeding episodes, determine frequency and dosage, describe concomitant medications and AHA diagnosis, and describe immunogenicity of Obizur during the course of routine treatment.

Research question and objectives:

The overall objective is to enroll patients with AHA who are prescribed and treated with Obizur, to assess safety, and to describe factors related to safety, utilization and effectiveness.

Study design:

This study is a multi-center, uncontrolled, open-label, non-interventional postauthorization safety surveillance study to describe the use of Obizur in patients with AHA, and secondarily, where data are available, to describe the hemostatic effectiveness and immunogenicity of Obizur. Approximately 40 male and female patients ≥18 years of age with AHA in the United States will be enrolled over a three and a half year period with follow-up from the date of treatment through 180 days; it is expected this prospective study will enroll up to two patients per month. Patients should be enrolled within five days of initiating Obizur to ensure unbiased prospective observation.

In addition, in an attempt to collect all safety and utilization data on patients treated with Obizur since Food and Drug Administration approval in October 2014, Baxalta will conduct a retrospective chart review on persons treated with Obizur prior to the prospective study start date. Baxalta expects there will be approximately 30 to 40 patients who were treated with Obizur prior to the study start date, on whom retrospective data will be collected.

Prospective data will be collected for each subject over a period of approximately 180 days from the time of Obizur treatment; in addition, data points that are retrospective in nature (such as comorbidities and prior medical treatment) will be obtained from the medical chart for the time period prior to Obizur treatment. A subject or a subject's legally authorized representative will provide signed informed consent according to local regulations, prior to data collection initiation. Signed informed consent should be obtained within five days of Obizur treatment for patients newly treated with Obizur.

Among patients in the retrospective cohort, for whom Obizur treatment occurred prior to initiation of the prospective study, signed informed consent will be obtained at the time the patient has a clinic visit. If the patient is deceased or lost to follow-up, only anonymized data will be collected from the medical chart and entered into the electronic data capture (EDC) system.

The choice of Obizur use is to be made *independent of and prior to* any decision by the subject or the subject's legally authorized representative to participate in this study. The treating physician will determine the treatment regimen, as well as frequency of laboratory and clinical assessments, according to routine clinical practice.

Data collection will be limited to existing information and for the purposes of this study will be collected if data are (a) part of routine clinical practice or (b) elected by an investigator. Available data from patient visits shall be entered into an EDC system and checked for data quality. Keeping with the non-interventional study design, there will be no *required* visits, medical tests, laboratory tests and/or procedures, or interventions during the study duration. Baxalta will provide the option for physicians to use a central laboratory to process anti-human and anti-porcine FVIII antibodies

If these assessments are made, it is recommended that a Bethesda assay using the Nijmegen modification be undertaken for antibodies measurement, and that pFVIII antibodies be tested before and during treatment administration, and in the follow-up. Lab results from local or other central laboratories available in the medical chart will be recorded; it is not a requirement of the study that these lab tests be completed.

Population:

In this study, Baxalta plans to enroll a prospective cohort of approximately 40 patients with AHA who have had a bleeding episode and are being newly treated with Obizur in a hospital setting. In addition, Baxalta will collect retrospective clinical data on AHA patients with a bleeding episode, who were treated with Obizur prior to the prospective study start date. Data elements for collection will be the same for both groups. The study will be conducted in the United States, and the majority of sites will be hematology departments, where patients are being treated by hematologists. Sites will be pre-selected and will obtain institutional review board (IRB) approval prior to subject enrollment.

The study enrollment and collection period will be 4 years in length; including start-up closure, and dissemination of the final report, the entire study will take approximately 4.5 years.

Variables:

- Demographics (age, sex, weight, race, ethnicity)
- Pregnant, breast-feeding, or post-partum
- Medical history
 - Bleed description
 - o spontaneous/traumatic, superficial/internal
 - location: intramuscular, retroperitoneal, gastrointestinal, intracranial, specify

- ➤ Hematology laboratory results (baseline and any follow-up)
 - Hemoglobin [<8 g/considered severe], hematocrit, red blood cell count, white blood cell count with differential, platelet count
- Bleed severity (baseline)
 - Physician assessment (severe/not severe)
- > FVIII activity levels (baseline)
- Anti-human and anti-porcine FVIII antibody titers (baseline)
- Prior treatment with hemostatic agents (baseline)
 - o Regimen received
 - Medication start/stop dates (retrospective cohort only)
- Comorbidities (baseline)
 - Physician assessment of association with AHA (possibly associated with causation of AHA/not associated with AHA)
- Current medications not related to AHA (taken within 14 days)
- ➤ AHA diagnosis
- Presentation of AHA symptoms
- Immunosuppressive agents received to treat underlying AHA during current Obizur treatment (baseline and follow-up)
- Obizur utilization (baseline and follow-up)
- Length of hospital stay per bleed (days)
- Safety (collect all SAEs; endpoint is therapy-related SAEs)
 - Key safety concerns:
 - o Inhibitor development against pFVIII (follow-up)
 - Hypersensitivity reactions including anaphylaxis
 - Thrombogenicity
 - Outcomes, including date of death
- Physician bleed cessation assessment
 - Bleeding stopped versus not stopped
 - Date bleeding stopped

- ➤ If bleeding not stopped, note reason (e.g., death, new treatment)
- FVIII activity measurements throughout treatment
- Human and porcine FVIII antibody titers. [Requirement to have a reference lab for anti-porcine FVIII antibody measurement (Central lab available if physician chooses to use it)]
- Concurrent bleeding episodes (baseline or follow-up)
 - Appearance of bleeding at a new site
- Treatment for bleeding episodes that occur greater than 72 hours after stopping treatment for the original bleed

Data sources:

Data wil be extracted from existing patient medical charts.

All prospective data shall be transcribed into the EDC system within 14 days of entry into the patient chart.

Retrospective data collection (for subjects who were treated with Obizur prior to initiation of the prospective study) will be completed within approximately 2 months of IRB approval.

Post-electronic data entry, medical dictionary for regulatory activities (MedDRA) coding will be conducted for all medical conditions reported and WHODRUG coding for all reported medications.

Study size:

There will be one cohort of approximately 40 patients with AHA who have had a bleeding episode and are being treated with Obizur. In addition, Baxalta expects there will be approximately 30 to 40 patients who were treated with Obizur prior to the initiation of the prospective study, on whom retrospective data will be collected.

Data analysis:

Sample Size Calculation

The proposed sample size of 40 patients will be adequate to address the primary objective of evaluating the safety profile for Obizur. No formal sample size calculations were performed for the determination of the number of subjects for documentation, as this is primarily a descriptive study and is not designed to test a specific statistical hypothesis.

Planned Statistical Analysis

The analysis plan for reports will be fully described in a written and approved statistical analysis plan (SAP). Descriptive statistics will include specifically, but not exclusively, arithmetic mean, medians, standard deviations, minimum, maximum, proportions, frequency counts, 25th and 75th percentiles, and 95% confidence intervals of select point estimates. Figures will be prepared to illustrate data patterns over time where appropriate. Analyses will be performed using available data, though missing values are expected due to the non-interventional nature of the study. Full details on handling missing data, which are common in observational studies, will be described separately in the SAP.

SAEs will be described in listings and tables, and incidence rates will be calculated. Tables outlining the hemostatic effectiveness and immunogenicity of Obizur, frequency, total dose, and total number of infusions of Obizur required to control bleeding episodes will be developed. Tables displaying concomitant medications and patient comorbidities will also be developed. Time from symptoms to diagnosis to treatment will be reported.

Milestones:

The study will either end 4 years from the time the first patient is enrolled, or will be assessed at the point 40 patients have been enrolled in the prospective portion of the study, whichever is earlier.

5. AMENDMENTS AND UPDATES

Not applicable.

6. MILESTONES

Milestone	Planned Date
Final protocol submission	31MAR2015
Start of all data collection/First site initiated	30SEP2015
Last subject in	31MAR2019
Last subject out	30SEP2019
Data lock for prospective data collection	01OCT2016
Data lock for prospective data collection	01OCT2017
Data lock for prospective data collection	01OCT2018
Data lock for prospective data collection, final report	31OCT2019
Data lock for Report on retrospective data	15DEC2015
Report on retrospective data results	30JAN2016
Annual study update report	15DEC2016
Annual study update report	15DEC2017
Annual study update report	15DEC2018
Final clinical study report	31JAN2020

7. RATIONALE AND BACKGROUND

7.1 Medicinal Product Safety Profile

Acquired hemophilia A (AHA) is a rare autoimmune disorder in which non hemophilic persons develop auto-antibodies directed against circulating blood coagulation factor (F) VIII. These auto-antibodies are distinct from the alloantibodies that form in patients with congenital hemophilia A in response to factor replacement therapy. In approximately 50% of cases FVIII autoantibodies occur in patients with no concomitant disease, while the remaining cases may be associated with an underlying medical condition such as pregnancy, hematological or solid tumors, infections, use of medications, or autoimmune diseases such as systemic lupus erythematosus, rheumatoid arthritis, and thyroid disorders. The estimated incidence rate of AHA is approximately one case per million persons annually, though it is likely that this figure is underestimated in the elderly population. This presumption is underscored by evidence indicating that the incidence of AHA increases with age. The incidence rate in children under 16 years is estimated to be 0.045 per million persons annually, compared to an estimated rate of 14.7 per million persons annually in individuals over 85 years of age.

Patients with AHA often experience serious subcutaneous bleeding episodes in the muscles or soft tissues and mucous membrane. This varies from the clinical manifestations of patients with congenital hemophilia A in which bleeds into the joint spaces are common.^{4,5} Severe bleeds occur in up to 90% of patients with AHA and may result in an estimated mortality rate due to bleeding ranging from 3% to 22%.²

Treatment for AHA focuses on treating and preventing the occurrence of bleeding episodes and eradicating the autoantibodies. Treatment choice is dependent on the site and severity of the hemorrhage, patient characteristics, concomitant disorders, and inhibitor titer.³ On the whole, treatment modalities include normalization of factor deficiency via pFVIII, plasma, or recombinant FVIII, bypassing inhibitor activity with recombinant activated FVII (rFVIIa) or activated prothrombin complex concentrates (aPCCs), neutralization of the autoantibodies by high-dose immunoglobulin, and removal of the pathogenic autoantibodies by plasmapheresis or immunoadsorption.

Bypassing agents such as rFVIIa and aPCCs are recommended as first-line treatment for acute bleeds due to demonstrated efficacy in the literature. ^{6,7,8} The choice of agent depends on several factors, including knowledge of the patient's previous response, convenience of dosing, use of plasma-derived products and cost. ⁹ Treatment with demopressin (DDVAP) may increase FVIII levels in some patients, though literature indicates that this treatment may be contraindicated in some patients due to

comorbidities. The international recommendations on the diagnosis and treatment of patients with AHA also recommend pFVIII as alternative therapy, however the drug was not available at the time of writing. Therefore, the authors indicated that the therapy may be added to an updated version of the guidelines after efficacy and safety had been established.

A recently developed highly purified antihemophilic recombinant porcine FVIII (rpFVIII) therapy (Obizur) was approved for the treatment of AHA. In AHA patients, Obizur temporarily replaces inhibited human FVIII with an rpFVIII based on the rationale that it is less susceptible to inactivation by circulating human FVIII antibodies. Twenty-nine adult subjects having autoimmune inhibitory antibodies to human FVIII and experiencing serious bleeding episodes that required hospitalization, were enrolled in a multi-center, prospective, open-label clinical trial that evaluated the safety and efficacy of Obizur. One of the subjects considered evaluable at study entry was later found to not have AHA, leaving 28 subjects evaluable for efficacy. Patients were treated with Obizur until resolution of bleeding or dosing was continued at the physician's discretion.

Each of the 28 evaluable patients with AHA showed an effective (bleeding stopped) or partially effective (bleeding reduced) response and clinical improvement at 24 hours after initial infusion. Additionally, a total of 86 percent (24/28) had successful treatment of the initial bleeding episode. Data from this study demonstrate an acceptable safety profile of Obizur. Of the ten subjects with detectable anti-porcine factor VIII antibodies at baseline, two (20%) experienced an increase in antibody titer, while eight experienced a decreasing to a non-detectable titer. Five of the 19 subjects that were negative for anti-porcine FVIII antibodies at baseline developed anti-porcine FVIII antibodies following exposure to Obizur. All subjects were also monitored for development of binding antibodies to baby hamster kidney (BHK) protein by a validated sequential ELISA (enzyme-linked immunosorbent assay). No patients developed *de novo* anti-BHK antibodies.¹⁰

7.2 Critical Review of Available Data

Data from the clinical trial demonstrated a positive safety and efficacy profile of pFVIII in patients with AHA, yet data are needed regarding safety and effectiveness of Obizur in the real-world setting. Therefore, Baxalta plans to conduct the present study to assess safety of Obizur based on incidence of related serious adverse events (SAEs) to describe the homeostatic effectiveness of Obizur in the treatment of bleeding episodes, determine frequency and dosage, describe concomitant medications and AHA diagnosis, and describe immunogenicity of Obizur during the course of routine treatment.

8. RESEARCH QUESTION AND OBJECTIVES

8.1 Research Question

The study is designed to assess safety and to describe factors related to the safety, utilization and effectiveness of Obizur in real-world clinical practice.

8.2 Primary Objective

The primary objective is to determine the incidence of therapy-related SAEs in patients with AHA who are prescribed and treated with Obizur in routine clinical practice.

8.3 Secondary Objectives

- 1. To describe hemostatic effectiveness of Obizur in the treatment of bleeding episodes.
- 2. To describe the frequency, total dose, and total number of infusions of Obizur required to control bleeding episodes.
- 3. To describe concomitant medication use.
- 4. To describe the clinical setting in which patients first present with symptoms of AHA, patient co-morbidities, time from presentation of symptoms to a positive diagnosis, and time from a positive diagnosis to first treatment with Obizur.
- 5. To describe the immunogenicity of Obizur during the course of treatment.

9. RESEARCH METHODS

9.1 Study Design

This study is a multi-center, uncontrolled, open-label, non-interventional postauthorization safety surveillance study to describe the use of Obizur in patients with AHA, and secondarily, where data are available, to describe the hemostatic effectiveness and immunogenicity of Obizur. Approximately 40 male and female patients ≥18 years of age with AHA in the United States will be enrolled over a 3.5 year period with follow-up from the date of treatment through 180 days; it is expected this prospective study will enroll up to two patients per month. Patients should be enrolled within five days of initiating Obizur to ensure unbiased prospective observation.

In addition, in an attempt to collect all safety and utilization data on patients treated with Obizur since Food and Drug Administration approval in October 2014, Baxalta will conduct a retrospective chart review on persons treated with Obizur prior to the prospective study start date. Baxalta expects there will be approximately 30 to 40 patients who were treated with Obizur prior to the study start date, on whom retrospective data will be collected.

Prospective data will be collected for each subject over a period of approximately 180 days from the time of Obizur treatment; in addition, data points that are retrospective in nature (such as comorbidities and prior medical treatment) will be obtained from the medical chart for the time period prior to Obizur treatment. A subject or a subject's legally authorized representative will provide signed informed consent according to local regulations, prior to data collection initiation. Signed informed consent should be obtained within five days of Obizur treatment for patients newly treated with Obizur.

Among patients in the retrospective cohort, for whom Obizur treatment occurred prior to initiation of the prospective study, signed informed consent will be obtained at the time the patient has a clinic visit. If the patient is deceased or lost to follow-up, only anonymized data will be collected from the medical chart and entered into the electronic data capture (EDC) system.

The choice of Obizur use is to be made *independent of and prior to* any decision by the subject or the subject's legally authorized representative to participate in this study. The treating physician will determine the treatment regimen, as well as frequency of laboratory and clinical assessments, according to routine clinical practice.

Data collection will be limited to existing information and for the purposes of this study will be collected if data are (a) part of routine clinical practice or (b) elected by an investigator. Available data from patient visits shall be entered into an EDC system and checked for data quality. Keeping with the non-interventional study design, there will be no *required* visits, medical tests, laboratory tests and/or procedures, or interventions during the study duration. Baxalta will provide the option for physicians to use a central laboratory to process anti-human and anti-porcine FVIII antibodies, should they choose to do so.

If these assessments are made, it is recommended that a Bethesda assay using the Nijmegen modification be undertaken for antibodies measurement, and that pFVIII antibodies be tested before and during treatment administration, and in the follow-up. Lab results from local or other central laboratories available in the medical chart will be recorded; it is not a requirement of the study that these lab tests be completed.

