9.2.4 Informed Consent and Enrollment

Any patient who provides informed consent (i.e., signs and dates the informed consent form and assent form, if applicable) is considered enrolled in the study. A legally authorized surrogate may also sign the informed consent. If the patient is deceased or lost to follow-up, only anonymized data will be collected from the medical chart and entered into the electronic data capture (EDC) system.

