10.4 Informed Consent

Investigators will choose patients for enrollment in consideration of the study eligibility criteria. The Investigator will exercise no selectivity so that no bias is introduced from this source.

All patients and/or their legally authorized representative must sign an ICF before entering into the study according to applicable regulatory requirements. Before use, the ICF will be reviewed by the MAH and approved by the EC and regulatory authority(ies), where applicable, (see Section 10.3). The ICF will include a comprehensive explanation of the study without any exculpatory statements, in accordance with the elements required by applicable regulatory requirements. Patients or their legally authorized representative(s) will be allowed sufficient time to consider participation in the study. By signing the informed consent form, patients or their legally authorized representative(s) agree to the use of their data for the study, unless they withdraw voluntarily or are terminated from the study for any reason.

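### The five-day consent window limits selection after exposure but cannot ensure unbiased observation, and the protocol is inconsistent on whether prospectively treated patients who die or are lost before consent are counted

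*Protocol*

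**What the plan says.** On timing, Section 9.1 sets the window and gives its purpose: "Patients should be enrolled within five days of initiating Obizur to ensure unbiased prospective observation". It adds: "Signed informed consent should be obtained within five days of Obizur treatment for patients newly treated with Obizur". The same section says that the subject or a legally authorised representative "will provide signed informed consent according to local regulations, prior to data collection initiation".

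On entry, Section 9.2.4 says that any patient who gives consent "is considered enrolled in the study", and it allows a surrogate to sign. Section 10.4 states: "All patients and/or their legally authorized representative must sign an ICF before entering into the study".

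On patients who cannot consent, Section 9.1 states: "If the patient is deceased or lost to follow-up, only anonymized data will be collected from the medical chart". There the sentence stands in the paragraph on the retrospective cohort, as it does in the abstract. Section 9.2.4, the general enrolment section, repeats it with no cohort named.

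On counting, Section 11.1.2 collects each SAE from the time of Obizur treatment. Section 9.7.3 defines the incidence proportion over the number of patients treated, and Section 9.7.1 puts all treated subjects in the analysis dataset. Section 9.5 allows for some retrospective patients to be assessed with the prospective cohort, raising the evaluable number from 40 to 50. Section 9.9 names only the difficulty of finding enough patients as a limitation.

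**The concern.** The risk period opens at first infusion, but a prospective patient exists in the study only once someone has signed. Entry is thus conditional on being alive and reachable, or having a representative available, until consent. A patient who dies or is lost in that interval can be absent from both numerator and denominator of the primary measure, although the stated denominator is patients treated. Unbiased observation is therefore not a property this design has.

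The study exists to measure the incidence of therapy-related SAEs in about 40 patients, so one or two uncounted patients matter. Sections 9.3.5 and 11.1.2 describe the population as often elderly, with many comorbidities and in intensive care, which makes some early loss plausible. If the anonymised route applies only to the retrospective cohort, that cohort keeps its deaths and losses while the prospective cohort drops those before consent. Pooling as in Section 9.5 would then mix two entry rules.

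**Working it through.** **1. Entry and counting rules side by side**

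| Element | Rule | Protocol section |
|---|---|---|
| Start of SAE collection | Obizur treatment | 11.1.2 |
| Denominator of incidence proportion | patients treated | 9.7.3 |
| Entry to the study | signed consent | 9.2.4, 10.4 |
| Latest consent, prospective | five days after treatment | 9.1 |
| Deceased or lost, no consent | anonymised chart, in the retrospective paragraph | 9.1 |
| Deceased or lost, no consent | anonymised chart, no cohort named | 9.2.4 |

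For a prospectively treated patient who dies on, say, day 2 with no form signed, Sections 9.1 and 10.4 point to exclusion. Sections 9.2.4 and 9.7.1, read literally, point to inclusion from the chart. Nothing in the protocol settles which applies.

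**2. The protocol's own precision figure**

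Clopper-Pearson limits with x events in n patients are: lower = Beta quantile(0.025; x, n − x + 1); upper = Beta quantile(0.975; x + 1, n − x). With n = 40 and x = 0.05 × 40 = 2 the limits are 0.61% and 16.92%. Section 9.5 gives 0.6% to 16.9%, so the figure is reproduced. It describes sampling error only and does not allow for patients missed before consent.

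**3. Adding missed patients back (illustration)**

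Suppose 2 of 40 enrolled patients have a related SAE, and k treated patients were missed, j of them with a related SAE. The incidence over all treated is (2 + j)/(40 + k). The values of k and j are assumptions.

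| k | j | Incidence | Upper 95% limit |
|---|---|---|---|
| 0 | 0 | 2/40 = 5.0% | 16.9% |
| 2 | 0 | 2/42 = 4.8% | 16.2% |
| 2 | 1 | 3/42 = 7.1% | 19.5% |
| 2 | 2 | 4/42 = 9.5% | 22.6% |
| 4 | 0 | 2/44 = 4.5% | 15.5% |
| 4 | 2 | 4/44 = 9.1% | 21.7% |
| 4 | 4 | 6/44 = 13.6% | 27.4% |

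Two missed means 2/42 = 4.8% of treated patients lost before consent; four missed means 4/44 = 9.1%.

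**4. Direction**

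Let e be the share of treated patients missed, q their risk of a related SAE, and p the risk among those enrolled. The incidence among all treated is (1 − e)p + eq, and the study observes p. The difference, all treated minus observed, is e(q − p).

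- q > p: the observed figure is too low. With p = 5%, e = 2% and q = 20%, the true value is 0.98 × 5% + 0.02 × 20% = 5.3%. With e = 10% and q = 100% it is 0.90 × 5% + 0.10 × 100% = 14.5%.
- q = p: no bias.
- q < p: the observed figure is too high. With e = 10% and q = 0 the true value is 0.90 × 5% = 4.5%, against 5.0% observed.

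The protocol gives neither e nor q.

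**The case against.** Several points on the other side are sound. The choice of Obizur must precede the decision to take part, so consent after exposure is built into a non-interventional design. The five-day cap limits the resulting selection and guards against enrolling patients once their outcome is known. Five days is a maximum, and consent on the day of treatment is possible. A representative may sign, which reduces loss from incapacity. Section 10.4 forbids investigator selectivity, and the log in Section 9.2.6 records reasons for non-enrolment. The study tests no hypothesis, and its interval is wide in any case. These points reduce the selection and its consequences. They do not restore a patient who dies or is lost before anyone signs, and the log alone does not bring that patient's SAEs into the incidence.

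Four stronger readings might be inferred, and the protocol does not support them:

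- **Such patients can never enter.** Section 9.2.4 gives the chart route without a cohort limit, and Section 9.7.1 includes all treated subjects. The text is in conflict; it does not state an exclusion.
- **The incidence is necessarily biased downward.** This requires q > p. The bleeding mortality of 3% to 22% in Section 7.1 has no time frame and is not a rate of therapy-related events. Losing patients whose deaths are judged unrelated would raise the estimate.
- **The days before consent are event-free person-time.** Section 11.1.2 captures SAEs from treatment, so enrolled patients contribute their early events as well as at most 5 of 180 days (2.8%). Starting person-time at consent would require those early events to be dropped from the rate, which would lose information.
- **The two cohorts are invalidly compared.** No comparison is planned, and Section 9.2.2 leaves their joint analysis to the SAP. The concern is limited to pooling under different entry rules.

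**Conclusion.** The concern stands in a limited form. Section 9.1 claims a property that the design lacks, because entry depends on consent that may follow exposure by up to five days while the primary incidence is defined over all treated patients from first infusion. Sections 9.1, 9.2.4 and 10.4 conflict on whether a prospectively treated patient who dies or is lost before consent is counted, and this affects the numerator and denominator of the primary measure.

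Neither the size nor the direction can be fixed from the protocol. With 2/40 observed, two missed patients would move 5.0% to between 4.8% and 9.5%, and four would move it to between 4.5% and 13.6%, depending on how many had a related SAE. These ranges rest wholly on assumed numbers of missed patients and events. The precision figures in Section 9.5 are correct as calculated.

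**What to change.** 1. Reconcile Sections 9.1, 9.2.4 and 10.4, and the matching abstract text, so that the anonymised-chart route, subject to IRB approval, also covers patients first treated at a site after its initiation who die or are lost before consent.
2. Use the Section 9.2.6 log to list every Obizur-treated patient at each site, with the reason for any non-enrolment.
3. Report the primary incidence with and without the non-consented patients, counting from first infusion. Do not count them toward the 40 that close enrolment under Section 9.2.8.
4. In Section 9.1 and the abstract, describe the window as limiting selection instead of ensuring unbiased observation, and list the residual selection in Section 9.9.

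The cost is a few extra chart abstractions and additional IRB wording. The protocol already foresees an anonymised route for the retrospective cohort, but extending it to prospectively treated patients is a separate ethics question and approval cannot be assumed. If it is refused, items 2 and 4 still apply, and the number of treated but non-enrolled patients should be reported beside the incidence. The change is best made before enrolment starts, because patients missed this way may not be recoverable later.
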